Q1	Regardless of your current level of sexual activity, please answer the following question. If you prefer not to answer it, please mark this box  and go to the next section.					
GS7	I am satisfied with my sex life	0	1	2	3	4

FACT-B (Version 4)

Please circle or mark one number per line to indicate your response as it applies to the past 7 days.

EMOTIONAL WELL-BEING		Not at all	A little bit	Some- what	Quite a bit	Very much
GE1	I feel sad	0	1	2	3	4
GE2	I am satisfied with how I am coping with my illness.....	0	1	2	3	4
GE3	I am losing hope in the fight against my illness	0	1	2	3	4
GE4	I feel nervous	0	1	2	3	4
GE5	I worry about dying	0	1	2	3	4
GE6	I worry that my condition will get worse	0	1	2	3	4

FUNCTIONAL WELL-BEING		Not at all	A little bit	Some- what	Quite a bit	Very much
GF1	I am able to work (include work at home)	0	1	2	3	4
GF2	My work (include work at home) is fulfilling.....	0	1	2	3	4
GF3	I am able to enjoy life.....	0	1	2	3	4
GF4	I have accepted my illness.....	0	1	2	3	4
GF5	I am sleeping well	0	1	2	3	4
GF6	I am enjoying the things I usually do for fun	0	1	2	3	4
GF7	I am content with the quality of my life right now.....	0	1	2	3	4

FACT-B (Version 4)

Please circle or mark one number per line to indicate your response as it applies to the past 7 days.

ADDITIONAL CONCERNS		Not at all	A little bit	Some- what	Quite a bit	Very much
B1	I have been short of breath.....	0	1	2	3	4
B2	I am self-conscious about the way I dress.....	0	1	2	3	4
B3	One or both of my arms are swollen or tender.....	0	1	2	3	4
B4	I feel sexually attractive	0	1	2	3	4
B5	I am bothered by hair loss	0	1	2	3	4
B6	I worry that other members of my family might someday get the same illness I have	0	1	2	3	4
B7	I worry about the effect of stress on my illness	0	1	2	3	4
B8	I am bothered by a change in weight	0	1	2	3	4
B9	I am able to feel like a woman	0	1	2	3	4
P2	I have certain parts of my body where I experience pain....	0	1	2	3	4

Table 2. Preliminary PROMIS Cancer Fatigue Short Form

Please respond to each question by checking one box

Item	In the Past 7 Days ...	Never	Rarely	Sometimes	Often	Always
FATEXP 20	How often did you feel tired?	 1	 2	 3	 4	 5
FATEXP 5	How often did you experience extreme exhaustion?	 1	 2	 3	 4	 5
FATEXP 18	How often did you run out of energy?	 1	 2	 3	 4	 5
FATIMP 33	How often did your fatigue limit you at work (include work at home)?	 1	 2	 3	 4	 5
FATIMP 30	How often were you too tired to think clearly?	 1	 2	 3	 4	 5
FATIMP 21	How often were you too tired to take a bath or shower?	 1	 2	 3	 4	 5
FATIMP 40	How often did you have enough energy to exercise strenuously?	 1	 2	 3	 4	 5

Abbreviations: PROMIS, Patient-Reported Outcomes Measurement Information System; FATEXP, Fatigue Experience; FATIMP, Fatigue Impact.
Reprinted with permission of the PROMIS Health Organization and the PROMIS Cooperative Group.

FACT-B (Version 4)

Below is a list of statements that other people with your illness have said are important. Please circle or mark one number per line to indicate your response as it applies to the past 7 days.

PHYSICAL WELL-BEING		Not at all	A little bit	Some- what	Quite a bit	Very much
GP1	I have a lack of energy	0	1	2	3	4
GP2	I have nausea	0	1	2	3	4
GP3	Because of my physical condition, I have trouble meeting the needs of my family	0	1	2	3	4
GP4	I have pain	0	1	2	3	4
GP5	I am bothered by side effects of treatment	0	1	2	3	4
GP6	I feel ill	0	1	2	3	4
GP7	I am forced to spend time in bed	0	1	2	3	4

SOCIAL/FAMILY WELL-BEING		Not at all	A little bit	Some- what	Quite a bit	Very much
GS1	I feel close to my friends	0	1	2	3	4
GS2	I get emotional support from my family	0	1	2	3	4
GS3	I get support from my friends	0	1	2	3	4
GS4	My family has accepted my illness	0	1	2	3	4
GS5	I am satisfied with family communication about my illness	0	1	2	3	4
GS6	I feel close to my partner (or the person who is my main support)	0	1	2	3	4
Q1	Regardless of your current level of sexual activity, please answer the following question. If you prefer not to answer it, please mark this box  and go to the next section.					
GS7	I am satisfied with my sex life	0	1	2	3	4

FACT-B (Version 4)

Please circle or mark one number per line to indicate your response as it applies to the past 7 days.

EMOTIONAL WELL-BEING		Not at all	A little bit	Some- what	Quite a bit	Very much
GE1	I feel sad	0	1	2	3	4
GE2	I am satisfied with how I am coping with my illness.....	0	1	2	3	4
GE3	I am losing hope in the fight against my illness	0	1	2	3	4
GE4	I feel nervous	0	1	2	3	4
GE5	I worry about dying	0	1	2	3	4
GE6	I worry that my condition will get worse	0	1	2	3	4

FUNCTIONAL WELL-BEING		Not at all	A little bit	Some- what	Quite a bit	Very much
GF1	I am able to work (include work at home)	0	1	2	3	4
GF2	My work (include work at home) is fulfilling.....	0	1	2	3	4
GF3	I am able to enjoy life.....	0	1	2	3	4
GF4	I have accepted my illness.....	0	1	2	3	4
GF5	I am sleeping well	0	1	2	3	4
GF6	I am enjoying the things I usually do for fun	0	1	2	3	4
GF7	I am content with the quality of my life right now.....	0	1	2	3	4

FACT-B (Version 4)

Please circle or mark one number per line to indicate your response as it applies to the past 7 days.

ADDITIONAL CONCERNS		Not at all	A little bit	Some- what	Quite a bit	Very much
B1	I have been short of breath.....	0	1	2	3	4
B2	I am self-conscious about the way I dress.....	0	1	2	3	4
B3	One or both of my arms are swollen or tender.....	0	1	2	3	4
B4	I feel sexually attractive	0	1	2	3	4
B5	I am bothered by hair loss	0	1	2	3	4
B6	I worry that other members of my family might someday get the same illness I have	0	1	2	3	4
B7	I worry about the effect of stress on my illness	0	1	2	3	4
B8	I am bothered by a change in weight	0	1	2	3	4
B9	I am able to feel like a woman	0	1	2	3	4
P2	I have certain parts of my body where I experience pain....	0	1	2	3	4

Table 2. Preliminary PROMIS Cancer Fatigue Short Form

Please respond to each question by checking one box

Item	In the Past 7 Days ...	Never	Rarely	Sometimes	Often	Always
FATEXP 20	How often did you feel tired?	 1	 2	 3	 4	 5
FATEXP 5	How often did you experience extreme exhaustion?	 1	 2	 3	 4	 5
FATEXP 18	How often did you run out of energy?	 1	 2	 3	 4	 5
FATIMP 33	How often did your fatigue limit you at work (include work at home)?	 1	 2	 3	 4	 5
FATIMP 30	How often were you too tired to think clearly?	 1	 2	 3	 4	 5
FATIMP 21	How often were you too tired to take a bath or shower?	 1	 2	 3	 4	 5
FATIMP 40	How often did you have enough energy to exercise strenuously?	 1	 2	 3	 4	 5

Abbreviations: PROMIS, Patient-Reported Outcomes Measurement Information System; FATEXP, Fatigue Experience; FATIMP, Fatigue Impact.
Reprinted with permission of the PROMIS Health Organization and the PROMIS Cooperative Group.

Checklist for Follow-up Visit:

Follow-up Labs: CBC w/diff, CMP, HbA1c Serum: IGF-1, adiponectin, leptin, estradiol, triglycerides, ESR, insulin, glucose	
Blood Sample sent to [name] lab for further analysis	
All Sections of CRF Completed	
FACT-B Completed by patient	
Weight, BMI, Body fat percent, bioimpedance	
Food diaries collected at this visit	

Please attach a copy of patient's labs when available.

**THOMAS JEFFERSON UNIVERSITY HOSPITAL
DEPARTMENT OF RADIATION ONCOLOGY**

CAREFOR Study: A Feasibility Pilot Trial Evaluating Caloric Restriction for Oncology Research
in Early Stage Breast Cancer Patients

WITHDRAWAL FORM

Patient Initials _____ MR# _____

Patient ID # _____

Please initial below:

_____ *I no longer wish to participate in this research study.*

_____ *I am withdrawing from the study treatment, but I agree to the research coordinator following up with me periodically to see how I am doing.*

Please sign below:

Patient: _____ Date: _____

Witnessed By: _____ Date: _____

**Thomas Jefferson University Hospital
Department of Radiation Oncology
CAREFOR Study**

Current Medication Flowsheet

Date Started	Medication	Indication	Route	Frequency	Dose	Date Stopped

Allergies:

Physician Signature: _____ **Date:** _____

Study : _____ Patient Case No. _____ Time Frame/Cycle #

(circle one): Y or N, N/A

Intermittent RT

Protocol Office AE Toxicity Flowsheet

Date AE Started	Brief Description of Event♦	Numeric Grade CTC 3.0	AEs	Attribution (Related to therapy)	AE Attribution (Potential cause)	Action (Check all that apply)	Outcome
Date:  New  F-U		 0  1  2  3  4	 AE  SAE	 Unrelated  Unlikely  Possible  Probable  Definite	 Chemotherapy  Radiation  Hormone-specify  Other _____	 none required  dose reduced*  dose held*  Adcers  IRB notified  MedWatch 3500A  Other _____	 Resolved End Date: _____  Ongoing
Date:  New  F-U		 0  1  2  3  4	 AE  SAE	 Unrelated  Unlikely  Possible  Probable  Definite	 Chemotherapy  Radiation  Hormone-specify  Other _____	 none required  dose reduced*  dose held*  Adcers  IRB notified  MedWatch 3500A  Other _____	 Resolved End Date: _____  Ongoing
Date:  New  F-U		 0  1  2  3  4	 AE  SAE	 Unrelated  Unlikely  Possible  Probable  Definite	 Chemotherapy  Radiation  Hormone-specify  Other _____	 none required  dose reduced*  dose held*  Adcers  IRB notified  MedWatch 3500A  Other _____	 Resolved End Date: _____  Ongoing
Date:  New  F-U		 0  1  2  3  4	 AE  SAE	 Unrelated  Unlikely  Possible  Probable  Definite	 Chemotherapy  Radiation  Hormone-specify  Other _____	 none required  dose reduced*  dose held*  Adcers  IRB notified  MedWatch 3500A  Other _____	 Resolved End Date: _____  Ongoing

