1.6 Dose Rationale and Risk/Benefits

The patients will undergo a 25% reduction in total caloric intake since this is a) the reduction used in other clinical trials that employ caloric restriction and, b) the definition of caloric restriction and the percent reduction noted to effect molecular targets in the IGF pathway.

The patients will undergo CR for a total of 10 weeks because previous studies have noted that the maximum effect of CR seems to be reached at 5 weeks. It is then important to incorporate at least 5 weeks for stabilization of physiologic processes

under caloric restriction [1].

The diet modification proposed should not induce many risks, and every effort will be made to insure that patients are receiving adequate overall nutrition. Although some patients may experience weight loss and fatigue, other risks should be minimal. These risks may include: decreased bone mineral density, decreased muscle mass and strength, depression, decreased sex drive, fatigue, irritability, fainting, rashes, acidosis, malnutrition, constipation, dehydration, cholelithiasis and reversible amenorrhea.

Because obesity has been proven a poor prognostic factor in those patients with breast cancer, dietary intervention may be ideal for improving outcomes for these patients who decrease their caloric intake.

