4.2 Exclusion Criteria

1. Patient is not a candidate for breast conservation.
2. Patient is male.
3. Age < 18 years
4. Patient requires regional lymph node irradiation therapy
5. Patient has evidence of distant metastases
6. Karnofsky Performance Status less than 80% within 60 days prior to study.
7. Ipsilateral mammogram done greater than 6 months prior to study.
8. Women of childbearing potential with a positive serum beta hCG.
9. Patient unable to consent or comply with study guidelines.
10. BMI < 21
11. Weight < 100 lbs
12. Unintentional weight loss $\geq 10\%$ in the last 3 mos

13. Prior invasive non-breast malignancy unless disease free for a minimum of 1 year prior to registration
14. Two or more breast cancers not resectable through a single lumpectomy incision
15. Non-epithelial breast malignancies such as sarcoma or lymphoma
16. Prior radiotherapy to the ipsilateral breast or prior radiation to the region of the breast that would result in overlap of radiation therapy fields
17. Severe, active co-morbidity, defined as follows:
 - Unstable angina and/or congestive heart failure requiring hospitalization within the last 6 months
 - Transmural myocardial infarction within the last 6 months
 - Acute bacterial or fungal infection requiring intravenous antibiotics at the time of registration;
 - Chronic Obstructive Pulmonary Disease exacerbation or other respiratory illness requiring hospitalization or precluding study therapy within 30 days before registration;
 - Hepatic insufficiency resulting in clinical jaundice and/or coagulation defects; note, however, that laboratory tests for liver function and coagulation parameters are not required for entry into this protocol
 - Acquired Immune Deficiency Syndrome (AIDS) or HIV positive based upon current CDC definition; note, however, that HIV testing is not required for entry into this protocol. The need to exclude patients with AIDS or HIV from this protocol is necessary because anti-retrivirals may alter patient metabolism.
18. Active systemic lupus erythematosus, or any history of active scleroderma, dermatomyositis with active rash
19. Active Gastrointestinal/Malabsorption disorder at the discretion of the Principal Investigator
 - Inflammatory Bowel Disease
 - Celiac Disease
 - Chronic Pancreatitis
 - Chronic Diarrhea or Vomiting
 - Active Eating Disorder
20. Current use of steroids
21. Active drug/alcohol dependence or abuse history.
22. Decisionally impaired patients.

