4.4 Subject Recruitment and Screening

Patients who are 18 year of age or older and are candidates for breast conservation for their breast cancer are eligible for the study. Patients can be recruited from the PI, co-investigators' or referring physician's clinical practices. We have designed a brochure to try and help with patient recruitment. This brochure is attached in the Appendix VIII Section. Potential study subject should be referred to PI or study designated research nurse/research associate. Appropriate laboratory or diagnostic testing necessary to meet any noted inclusion or exclusion criteria will be ordered

through the recruiting physician. PI of the study or study designated research nurse/research associate will screen and determine the final eligibility of the subject for enrollment.

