Appendix VII. Case Report Forms

THOMAS JEFFERSON UNIVERSITY HOSPITAL DEPARTMENT OF RADIATION ONCOLOGY

CAREFOR Study: A Feasibility Pilot Trial Evaluating Caloric Restriction for Oncology Research
in Early Stage Breast Cancer Patients

REGISTRATION FORM

Patient's Initials_____ Case#_____ Dose Level_____

MR#_____ Date of birth_____

Address_____

Telephone_____

Sex_____ Race_____ Ethnicity_____

Insurance_____

Radiation Oncologist:_____

Medical Oncologist:_____

Resident:_____

Signature_____ Date_____

CAREFOR Study Case Report Form (CRF)—Screening Visit

Date of Screening: _____

Patient Demographics

Age: _____ Race: _____

Current Address (for mailing purposes):

Emergency Contact: _____

Marital Status: _____

Highest Education Level Completed: _____

Past Medical History and Relevant Clinical Information

Date of Diagnosis: _____

How was the mass found?

- MMG
- SBE
- Physician Exam
- Other: _____

Date of most recent mammogram: _____

Side of Breast Mass (L v. R): _____

Previous History of Breast Cancer: _____

Family History of Breast Cancer: _____

If applicable, what treatment was received for previous breast cancer: _____

_____ Previous History of any
other malignancy (include dates of diagnosis and NED date): _____

Is this patient a candidate for breast conservation? _____
_____ Oral

Contraceptive Use (current or past): Y or N

Hormone Replacement Use: Y or N

Date of last period _____ Age at menarche: _____

Gravida/Para: _____

Previous diagnosis of any of the following:

- Unstable Angina
- Coronary Artery Disease

Myocardial Infarct, if yes please indicate date of event: _____

CHF

Valvular Disease

Arrhythmias/Pacemaker Placement

Diabetes

Severe Asthma

Autoimmune Disorder (specifically SLE, scleroderma, dermatomyositis)

Any Disease Requiring Chronic Steroid Use

Inflammatory Bowel Disease

Celiac Disease

Chronic Pancreatitis

Chronic Diarrhea or Vomiting

Active Eating Disorder

Renal Failure or CKD

Pituitary Secreting Tumor

HIV Positive Status or AIDS including any AIDS defining illness

Hepatic Insufficiency

Recent hospitalization (within the last 6 months, include diagnosis and length of stay): _____

Recent Weight Loss (include baseline weight and pounds lost): _____

Surgical History

Please indicate any major surgeries, the date or at least the year of the surgery and whether or not there were any post-op complications:

Surgery Date

Pre-op Diagnosis

Post-Op Complications

Pertinent Social History

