- ❖ Stay willing and open to change. Always "hang in there."

You can count on me to:

- ❖ Go over your records of what you eat and your activity.
Notice what you are doing well and what can be improved.
- ❖ Answer your questions.
- ❖ Be honest.
- ❖ Stand by you during hard times.
- ❖ Believe you can reach your eating and activity goals.
Always "hang in there" for you. Support and help you.

We agree to work together in the ways described above.

Signed: _____

**Thomas Jefferson University
Kimmel Cancer Center**

CAREFOR Inclusion/Exclusion Criteria Checklist

Inclusion Criteria:

Patients must meet all of the following criteria in order to be considered for entry into the CAREFOR trial.

- Pathologically confirmed diagnosis of DCIS or invasive breast cancer
- Female patient, 18 years or older
- Candidate for breast conservation
- Karnofsky performance status at least 80%
- Negative serum beta-hCG if appropriate
- Willing to use contraception, not sexually active or post-menopausal
- BMI > 21
- Weight > 100lbs

Exclusion Criteria:

In addition to meeting inclusion criteria, patients are ineligible for enrollment if any of the following exclusion criteria are met.

- Intentional weight loss > 10% of total body weight within the last 3 months prior to trial enrollment.
- Prior non-breast invasive malignancy, unless free of disease for at least 1 year prior to trial enrollment.
- Two or more breast cancers not resectable through a single lumpectomy site.
- Non-epithelial breast malignancies such as sarcoma or lymphoma.
- Prior radiotherapy to ipsilateral breast that would result in overlapping radiation fields.
- Severe, active comorbidities to include any one of the following:
 - Unstable angina or CHF requiring hospitalization in the last 6 months
 - COPD exacerbation requiring hospitalization within 30 days of registration
 - Transmural myocardial infarct in the past 6 months
 - Acute bacterial or fungal infection requiring IV antibiotics at the time of registration

- Hepatic insufficiency resulting in clinical jaundice
- AIDS or HIV positive according to CDC guidelines
- Active systemic lupus erythematosus, scleroderma or dermatomyositis with rash.
- Medical or psychiatric condition preventing the patient from providing informed consent or from adhering to diet guidelines.
- Currently taking diet supplements
- Active gastrointestinal/malabsorption syndrome to include:
 - Inflammatory Bowel Disease
 - Celiac Disease
 - Chronic Pancreatitis

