 - Chronic Diarrhea or Vomiting
 - Active Eating Disorder
- Currently using steroids
-
- Active/history of substance abuse or dependency to include prescription or illicit drugs as well as alcohol.
- Decisionally impaired patients.

Checklist for Screening Visit:

Informed Consent for Trial Obtained	
All Sections of CRF Completed	
Inclusion/Exclusion Criteria Evaluated	
Blood draw: Beta-HCG	
H&P; Performance Status	
Weight, BMI	
Based on screening patient appears eligible	

CAREFOR Study Case Report Form (CRF)—Radiation Treatment Planning Visit

Date of Sim Visit: _____

Lumpectomy Details

Please indicate the actual date of the lumpectomy, whether or not there were any post-op complications and the status of the Path report:

Surgery DatePre-op DiagnosisPost-Op Complications_____

Path Report Received? Y or N

Attach a copy of the Path Report to this visit.

Verify Allergies:_____

_____**Changes to Current Medications (indicate dose, route, frequency and start date):**

Medication

Dose

Route

Frequency

Start Date

Physical Examination

Height: _____ Weight: _____ BMI: _____
 Vital Signs: BP: _____ HR: _____ Temp: _____ RR: _____
 Caliper Measurements: _____

Bioimpedance Measurement: _____

Please indicate the status (normal or abnormal) of each system listed below. If abnormal, please make notes. Give detailed description of breast exam in the notes section.

Organ System	Status	Notes
CVS	Normal Abnormal	_____
Pulm	Normal Abnormal	_____ _____
GI	Normal Abnormal	_____ _____
Neuro	Normal Abnormal	_____ _____
Breast	Normal Abnormal	_____ _____ _____

CTCAE v4.0 Evaluation

Please evaluate the patient at baseline for comparison during and post-radiation.

Adverse Event	Grade				
	1	2	3	4	5
Dermatitis radiation	Faint erythema or dry desquamation	Moderate to brisk erythema; patchy moist desquamation, mostly confined to skin folds and creases; moderate edema	Moist desquamation in areas other than skin folds and creases; bleeding induced by minor trauma or abrasion	Life-threatening consequences; skin necrosis or ulceration of full thickness dermis; spontaneous bleeding from involved site; skin graft indicated	Death
Definition: A finding of cutaneous inflammatory reaction occurring as a result of exposure to biologically effective levels of ionizing radiation.					
Skin hyperpigmentation	Hyperpigmentation covering <10% BSA; no psychosocial impact	Hyperpigmentation covering >10% BSA; associated psychosocial impact	-	-	-

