- *Patient must not have active systemic lupus, erythematosus, or any history of scleroderma, dermatomyositis with active rash*
- *No prior radiotherapy to the ipsilateral breast or prior radiation to the region of the breast that would result in overlap of radiation therapy fields*
- *Patient may not have any active Gastrointestinal/Malabsorption disorder at the discretion of the Principal Investigator*
 - *Inflammatory Bowel Disease*
 - *Celiac Disease*
 - *Chronic Pancreatitis*
 - *Chronic Diarrhea or Vomiting*
 - *Active Eating Disorder*
-
- *Not currently taking steroids*
- *No history of or current active drug/alcohol dependence.*
- *No patients with decisional impairment.*

Exclusion Criteria

- *Patient is not a candidate for breast conservation.*
- *Patient is male.*
- *Age <18 years*
- *Patient has evidence of distant metastases*
- *Karnofsky Performance Status less than 80% within 60 days prior to study.*
- *Ipsilateral mammogram done greater than 6 months prior to study.*
- *Women of childbearing potential with a positive serum beta hCG.*
- *Patient has a history of dementia, psychosis or other disorder affecting their mental status to the point where they cannot consent or comply with study guidelines.*
- *BMI < 21*
- *Weight < 100lbs*
- *Unintentional weight loss ≥10% in the last 3 mos*
- *Prior invasive non-breast malignancy (except non-melanomatous skin cancer, carcinoma in situ of the cervix) unless disease free for a minimum of 2 years prior to registration*

- Two or more breast cancers not resectable through a single lumpectomy incision*
- Non-epithelial breast malignancies such as sarcoma or lymphoma*
- Prior radiotherapy to the ipsilateral breast or prior radiation to the region of the breast that would result in overlap of radiation therapy fields*
- Severe, active co-morbidity, defined as follows:*
 - Unstable angina and/or congestive heart failure requiring hospitalization within the last 6 months*
 - Transmural myocardial infarction within the last 6 months*
 - Acute bacterial or fungal infection requiring intravenous antibiotics at the time of registration;*
 - Chronic Obstructive Pulmonary Disease exacerbation or other respiratory illness requiring hospitalization or precluding study therapy within 30 days before registration;*

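### The Appendix VII screening checklist excludes intentional weight loss where Section 4.2 excludes unintentional loss, so read literally it passes the patients the criterion should stop

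*Combined protocol and SAP*

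**What the plan says.** The weight-loss exclusion appears in three places.

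- **Section 4.2, item 12** excludes "Unintentional weight loss" of at least 10% over the last 3 months.
- **Appendix X**, exclusion list, agrees: "Unintentional weight loss ≥10% in the last 3 mos".
- **Appendix VII**, inclusion/exclusion checklist, excludes "Intentional weight loss > 10% of total body weight within the last 3 months prior to trial enrollment".

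The Appendix VII checklist states that meeting any one listed exclusion makes a patient ineligible. The screening-visit list that follows it has tick entries for "Inclusion/Exclusion Criteria Evaluated" and "Based on screening patient appears eligible". Section 4.4 allows either the principal investigator or a delegate to decide: the designated research "nurse/research associate will screen and determine the final eligibility of the subject for enrollment". The screening case report form has a weight-loss field, "Recent Weight Loss (include baseline weight and pounds lost", which asks for neither the reason for the loss nor the period over which it occurred.

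**The concern.** The intervention is a 25% cut in calories for about 10 weeks. Section 1.6 expects some weight loss from it: "Although some patients may experience weight loss and fatigue, other risks should be minimal". Section 5.3 lists weight loss among the likely risks and malnutrition among the rare ones. Against that background, excluding women who have recently lost 10% of their weight without trying is most naturally read as a safety criterion, although the protocol does not give its reason.

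The Appendix VII form turns that criterion round. A patient with unintentional loss is not flagged by the weight-loss item, while a patient who dieted deliberately is turned away although Section 4 does not exclude her. Nothing in the documents explains a deliberate switch. Even if an exclusion for intentional loss were wanted, the form would still lack the one for unintentional loss.

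**Working it through.** The plan gives no figure to reproduce here. The check is a comparison of texts, followed by one piece of arithmetic on the form's other items.

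**1. The three versions applied to the same patients (loss within 3 months)**

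| Patient | Section 4.2 item 12 | Appendix X | Appendix VII weight-loss item |
|---|---|---|---|
| 12% loss, unintentional | excluded | excluded | not flagged |
| 12% loss, intentional | not excluded | not excluded | excluded |
| exactly 10%, unintentional | excluded | excluded | not flagged |
| exactly 10%, intentional | not excluded | not excluded | not flagged |

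The threshold differs as well: at least 10% in Section 4.2 and Appendix X, strictly more than 10% in Appendix VII.

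**2. Do the form's weight and BMI floors compensate?**

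Inputs from the Appendix VII inclusion list: weight above 100 lb and BMI above 21. A patient who has lost a fraction L of her weight ends at or below a floor only if her starting value was at or below floor / (1 − L).

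| Loss L | Starting weight stopped by the floor | Starting BMI stopped by the floor |
|---|---|---|
| 10% | 100/0.90 = 111.1 lb | 21/0.90 = 23.3 |
| 15% | 100/0.85 = 117.6 lb | 21/0.85 = 24.7 |
| 20% | 100/0.80 = 125.0 lb | 21/0.80 = 26.25 |

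A patient who started above both values passes the weight-loss, weight and BMI items. As an illustration with assumed values, a woman of 160 lb and BMI 28 who loses 12% unintentionally ends at 160 × 0.88 = 140.8 lb and BMI 28 × 0.88 = 24.6, and passes all three.

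**3. Other mismatches with Section 4 (selected, not a full list)**

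- Neither checklist carries the exclusion for regional nodal irradiation (Section 4.2 item 4). The risk is low: the radiation oncologist makes that decision under Section 4.1 item 2, and Section 6.4.1 gives doses only for the breast and the lumpectomy cavity.
- The Appendix VII checklist lacks the exclusions for distant metastases and mammogram date (items 5 and 7). The mammogram date is recorded on the screening form, and Section 6.2.1 verifies clinical staging.
- For prior non-breast malignancy, Appendix X gives 1 year in its inclusion list and 2 years in its exclusion list. Section 4 gives 1 year.

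**The case against.** The strongest reply is that harm needs more than one failure. Section 4 requires the principal investigator to review baseline results before enrollment and confirm that every criterion is met. Section 6.2.1 verifies eligibility against the criteria already stated, and a full history and physical examination is done. Appendix X has the right wording. The tick entry on the Appendix VII screening list is provisional. Any recent weight loss is written on the case report form, so it can reach the investigator.

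The Appendix VII form also excludes several conditions that could cause weight loss, such as malabsorptive disease, chronic diarrhea or vomiting, and an active eating disorder, and it requires a Karnofsky score of at least 80%. Once on study, the diet is tailored by a physician and weight is measured repeatedly.

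These safeguards are real and limit the consequence to literal use of the form. They do not remove it. The case report form field gives the reviewer neither intent nor period, so item 12 cannot be applied from that field alone. The other exclusions catch some causes of weight loss, not the loss itself. On-study weighing and the random audit in Section 10.2.1, which covers at least 10% of patients already entered, act only after entry. The documents do not say which of the two checklists is operative.

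It is also fair to say that the safety purpose of item 12 is inferred, and that this is an inconsistency between documents rather than a flaw in the statistical design.

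**Conclusion.** The concern holds. One eligibility exclusion is reversed on a working screening form, in conflict with Section 4.2 and Appendix X. The error runs in both directions: it can admit a patient whom the protocol bars and reject one whom it allows.

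The conclusion about safety rests on two assumptions: that the form is used as written, and that item 12 is meant to protect patients from further calorie restriction after unintentional loss. How many patients would be affected cannot be worked out from the documents. Sample size, power, alpha and the analyses are untouched. The correction should be made because the cost is very small and the criterion bears on patient safety.

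**What to change.** 1. In the Appendix VII checklist, replace the weight-loss item with the Section 4.2 criterion: unintentional loss, at least 10%, last 3 months.
2. In the weight-loss field of the screening case report form, add whether the loss was intentional and over what period it occurred.
3. Add the nodal-irradiation exclusion to both checklists, and the distant-metastasis and mammogram-date exclusions to the Appendix VII checklist. Change 2 years to 1 year in the Appendix X prior-malignancy exclusion.
4. Preferably, keep a single checklist taken directly from Section 4 and name it as the operative form. That would also clear the smaller differences not listed here.

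Items 1 to 3 are wording edits to two checklists and one form field, submitted to the IRB as an amendment under Section 11. They add no visits or procedures and leave the eligible population defined in Section 4 unchanged.
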